4.5.2.2 Storage and coding of DNA samples

The DNA samples will be retained by the extraction laboratory. The DNA samples will be stored for 2 years after database lock and then destroyed. The blood sample for CYP2C19 genotyping will be coded with enrollment code. No personal details identifying the individual will be available to any employee working with the DNA.

4.5.2.3 CYP2C19 genotyping

The CYP2C19 metabolizer status will be derived from the CYP2C19 genotype using the Amplichip CYP450 Test or another agreed and validated test used by the agreed extraction laboratory vendor. Additional methods, such as direct sequencing and electrophoresis, may also be used to determine, or further refine, the CYP2C19 genotype. These analyses will be conducted for randomization purposes only.

4.6 Volume of blood sampling

The total volume of blood that will be drawn from each subject in this study is as follows:

Table 4 Volume of blood to be drawn from each subject

Assessment	Sample volume (mL)	n of samples	Total volume (mL)
Blood sampling for rosuvastain	4 mL	35	140 mL
Genetic sample	9 mL	1	9 mL
Lipid profile	10 mL	2	20 mL
Safety HIV/HbsAG/ Hep C	10 mL	1	10 mL
Clinical chemistry	10 mL	3	30 mL
Hematology	10 mL	3	30 mL
Total		45	239 mL

4.7 Adverse Events

The methods for collecting adverse events are described below.

4.7.1 Adverse Events

4.7.1.1 Definitions

The definitions of adverse events (AEs), serious adverse events (SAEs) and other significant adverse events (OAEs) are given below. It is of the utmost importance that all staff involved in the study is familiar with the content of this section. The principal investigator is responsible for ensuring this.

Adverse event

An AE is the development of an undesirable medical condition or the deterioration of a pre-existing medical condition following or during exposure to a pharmaceutical product, whether or not considered causally related to the product. An undesirable medical condition can be symptoms (eg, nausea, chest pain), signs (eg, tachycardia, enlarged liver) or the abnormal results of an investigation (e.g., laboratory findings, electrocardiogram). In clinical studies, an AE can include an undesirable medical condition occurring at any time, including run-in or washout periods, even if no study treatment has been administered.

Serious adverse event

A SAE is an AE occurring during any study phase (i.e., run-in, treatment, washout, follow-up), and at any dose of the investigational product, comparator or placebo, that fulfills one or more of the following criteria:

- Results in death
- Is immediately life-threatening
- Requires in-patient hospitalization or prolongation of existing hospitalization
- Results in persistent or significant disability or incapacity
- Is a congenital abnormality or birth defect
- Is an important medical event that may jeopardize the subject or may require medical intervention to prevent one of the outcomes listed above.

The causality of SAEs (ie, their relationship to study treatment) will be assessed by the investigator(s), who, in completing the relevant case report form, must answer “yes” or “no” to the question “Do you consider that there is a reasonable possibility that the event may have been caused by any of the following – study medication – other medication?”. For further guidance on the definition of a SAE and a guide to the interpretation of the causality question, see [Appendix B](#) to the Clinical Pharmacology Study Protocol.

Note that SAEs that could be associated with any study procedure should also be reported. For such events the causal relationship is implied as “yes”.

Other Significant Adverse Events (OAE)

OAEs will be identified by the Study Delivery Team Physician in consultation with the appropriate Global Drug Safety Physician during the evaluation of safety data for the Clinical Study Report. Significant adverse events of particular clinical importance, other than SAEs and those AEs leading to discontinuation of the subject from study treatment, will be classified as OAEs. Examples of these are marked hematological and other laboratory abnormalities, and certain events that lead to intervention (other than those already classified as serious), dose reduction or significant additional treatment. For each OAE, a narrative may be written and included in the Clinical Study Report.

4.7.1.2 Recording of adverse events

The following variables will be recorded for each AE:

Start date, stop date, maximum intensity, action taken, outcome, causality (yes or no) and whether it constitutes an SAE or not.

The intensity rating is defined as:

- mild (awareness of sign or symptom, but easily tolerated)
- moderate (discomfort sufficient to cause interference with normal activities)
- severe (incapacitating, with inability to perform normal activities)

It is important to distinguish between serious and severe AEs. Severity is a measure of intensity whereas seriousness is defined by the criteria in Section 4.7.1.1. An AE of severe intensity need not necessarily be considered serious. For example, nausea that persists for several hours may be considered severe nausea, but not a SAE. On the other hand, a stroke that results in only a limited degree of disability may be considered a mild stroke but would be a SAE.

Should an overdose (accidental or deliberate) occur, it must be reported in accordance with the procedures described in Section 8.3, regardless of whether the overdose was associated with any symptom or not. All symptoms associated with the overdose should be reported as AEs.

Should a pregnancy occur, it must be reported in accordance with the procedures described in Section 8.4. Pregnancy in itself is not regarded as an AE unless there is a suspicion that an investigational product may have interfered with the effectiveness of a contraceptive medication.

4.7.1.3 Reporting of serious adverse events

Investigators and other site personnel must inform appropriate AstraZeneca representatives of any SAE that occurs in the course of the study within 1 day (i.e., immediately but no later than the end of the next business day) of when he or she becomes aware of it.

The AstraZeneca representative will work with the investigator to compile all the necessary information and ensure that the appropriate AstraZeneca Drug Safety Department receives a report by day one for all fatal and life-threatening cases and by day five for all other SAEs.

Follow-up information on SAEs must also be reported by the investigator within the same time frames.

If a non-serious AE becomes serious, this and other relevant follow-up information must also be provided to AstraZeneca within 1 day as described above. For a non-serious AE that become serious but which is not fatal or life-threatening a report should be received within 5 days.

All SAEs have to be reported, whether or not considered causally related to the investigational product or to the study procedure(s). All SAEs will be recorded in the CRF. The investigator and/or Sponsor are responsible for informing the Ethics Committee and/or the Regulatory Authority of the SAE as per local requirements.

5. STUDY MANAGEMENT

5.1 Monitoring

5.1.1 Study monitoring

The monitoring of this study will be performed in accordance with the principles of Good Clinical Practice (GCP) as laid out in the International Conference on Harmonization (ICH) document “Good Clinical Practice: Consolidated Guideline”.

The specific requirements of the genetic part of the study will be discussed with the investigator and other personnel involved with the study.

5.1.2 Data verification

It is a prerequisite of this study that the study monitor has direct access to source data for data verification. This will be done by comparing data from the CRFs with those in the subject’s medical notes (permission from the subject will be sought as part of the consent process). Such verification is an essential element of quality control, as it allows the rectification of transcription errors and omissions.

Monitoring including source data verification should routinely be performed prior to the transfer of data to Data Management.

Source verification of the study/genetic informed consent of participating subjects will be performed and to make sure that the investigational team is adhering to the specific requirements of the genetics aspects of the study.

5.2 Audits and inspections

Authorized representatives of AstraZeneca, a regulatory authority, an Ethics Committee may visit the center to perform audits or inspections, including source data verification. The purpose of an AstraZeneca audit or inspection is to systematically and independently examine all study-related activities and documents to determine whether these activities were conducted, and data were recorded, analyzed, and accurately reported according to the protocol, GCP guidelines of the ICH and any applicable regulatory requirements. The investigator should contact AstraZeneca immediately if contacted by a regulatory agency about an inspection at his or her center.

5.3 Training of staff

The principal investigator will maintain a record of all individuals involved in the study (medical, nursing and other staff). He or she will ensure that appropriate training relevant to the study is given to all of these staff, and that any new information of relevance to the performance of this study is forwarded to the staff involved.

Before the first subject is entered into the study the investigational staff will have an opportunity to discuss the procedures associated with the collection of blood samples, extraction of DNA and genetic testing with AstraZeneca personnel. The ethical considerations specific to genotyping and the importance of the informed consent process will be made clear. The requirements for the collections of the subjects' samples will also be made clear.

5.4 Changes to the protocol

Study procedures will not be changed without the mutual agreement of the principal investigator and AstraZeneca.

If it is necessary for the study protocol to be amended, the amendment and/or a new version of the study protocol must be notified to or approved by each Ethics Committee, and in many countries also the local regulatory authority, before implementation. Local requirements must be followed.

If an administrative change is required, such a change must be notified to or approved by each Ethics Committee according to local requirements.

If a protocol amendment requires a change to a particular center's Informed Consent Form, then AstraZeneca and the center's Ethics Committee must be notified. Approval of the revised Master Informed Consent Form by AstraZeneca and by the Ethics Committee is required before the revised form is used.

AstraZeneca will distribute amendments and new versions of the protocol to each principal investigator(s) who in turn is responsible for the distribution of these documents to his or her Ethics Committee, and to the staff at his or her center. The distribution of these documents to the regulatory authority will be handled according to local practice.

5.5 Study agreements

The principal investigator must comply with all the terms, conditions, and obligations of the study agreement for this study. In the event of any inconsistency between this protocol and the study agreement, this protocol shall prevail.

5.6 Study timetable and end of study

The study is expected to start in _____ and to be completed by _____.

5.7 Data management

5.7.1 Case report forms

Paper CRFs (pCRFs) or Electronic (eCRFs) will be used to record all data. If using pCRFs, data should be recorded legibly onto the pCRFs in blue or black ballpoint pen. Correction fluid or covering labels must not be used.

The monitor will check data at the monitoring visits to the study site. The Investigator will ensure that the data in the pCRFs or entered in the eCRF system are accurate, complete and legible.

Data from the completed pCRFs will be entered into the clinical study database and validated under the direction of the Data Manager. If data are entered directly into an Electronic CRF system the data will be monitored against the source verification documents. Any missing, impossible or inconsistent recordings in the pCRFs/eCRFs will be referred back to the Investigator using a data query form (paper or electronic) and be documented for each individual subject before clean file status is declared.

5.7.2 Genetic data

In the case of genotypic data, the date the subject gave consent to participate in the study and the date the blood sample was taken from the subject will be recorded in the pCRF and database.

5.8 Reporting of genotypic results

The CYP2C19 genotype (PM or EM) will be reported back to the investigator to be used in randomization of the subjects and will not be routinely reported to the participating subjects.

Individual subjects will not be identified in any report or publication resulting from this work. The data and results of this study may be reviewed with collaborators and published, but neither the subject's name nor any other personal identifiers will appear in any publication or report.

6. PHARMACOKINETIC, PHARMACODYNAMIC, SAFETY, GENETIC AND STATISTICAL METHODOLOGY

6.1 Pharmacokinetic / pharmacodynamic evaluation

6.1.1 Calculation or derivation of pharmacokinetic variables

The Clinical Pharmacokinetics Group, AstraZeneca, Wilmington, Delaware will carry out the pharmacokinetic analyses.

The pharmacokinetic variables of rosuvastatin, N-desmethyl rosuvastatin, and rosuvastatin lactone defined below will be calculated by non-compartmental methods using WinNonlin Enterprise version 4.1, Pharsight Corp., Mountain View, CA. The actual sampling times will be used in the pharmacokinetic calculations. The following parameters will be derived:

The primary variables to be assessed for rosuvastatin after a single dose are:

- C_{\max} - the observed maximum plasma concentration following a single dose
- AUC - area under the plasma concentration time curve, calculated by $AUC_{(0-t)}$ and then extrapolated to infinity by the addition of $(C_{\text{last}} / \lambda_z)$
- $AUC_{(0-t)}$ - area under the plasma concentration time curve from time zero to the last quantifiable plasma concentration (C_{last}), calculated using the linear trapezoidal rule
- AUMC - area under the first moment curve; AUMC will be calculated by the linear trapezoidal rule
- t_{\max} - the time to reach the observed maximum plasma concentration following a single dose
- λ_z - terminal elimination rate constant, calculated by log-linear regression of the terminal portion of the concentration time profile where there are sufficient data (a minimum of 3 plasma concentration values in the terminal log-linear phase, spanning an interval of at least 2 half-lives)
- $t_{1/2, \lambda_z}$ - half-life associated with the terminal slope (λ_z) of a semi logarithmic plasma concentration-time curve. Calculated as $\ln(2)/\lambda_z$
- MRT - mean residence time; calculated as $AUMC/AUC$
- CL/F - apparent oral clearance, calculated as Dose/AUC (rosuvastatin only). If for an individual, AUC cannot be calculated CL/F will not be calculated.
- Vd/F - volume of distribution (apparent) during terminal (λ_z) phase; calculated as $\text{Dose}/AUC * \lambda_z$; (rosuvastatin only)

The primary variables to be assessed for rosuvastatin after multiple dosing are:

- $C_{ss,max}$ - maximum (peak) steady state drug concentration in plasma during steady state dosing interval
- $C_{ss,min}$ - minimum (trough) steady state drug concentration in plasma during steady state dosing interval
- $C_{ss,av}$ - average drug concentration in plasma during a dosing interval at steady station on administering a fixed dose at equal dosing intervals; calculated as AUC_{ss}/τ
- $t_{ss,max}$ - the time to reach the observed maximum plasma concentration at steady-state
- $t_{ss,1/2}$ - the apparent terminal half-life at steady-state
- AUC_{ss} - area under the plasma concentration time curve during any dosing interval at steady state; calculated using the linear trapezoidal rule
- DF - degree of fluctuation; calculated as $(C_{ss,max} - C_{ss,min})/C_{ss,av} * 100\%$
- AR - accumulation ratio; calculated as $AUC_{(0-24)}(\text{Day 17})/AUC_{(0-24)}(\text{Day 1})$

The secondary variables to be assessed for rosuvastatin metabolites N-desmethyl rosuvastatin and rosuvastatin lactone after a single dose are:

- C_{max} - the observed maximum plasma concentration following a single dose
- AUC - area under the plasma concentration time curve, calculated by $AUC_{(0-t)}$ and then extrapolated to infinity by the addition of (C_{last} / λ_z)
- $AUC_{(0-t)}$ - area under the plasma concentration time curve from time zero to the last quantifiable plasma concentration (C_{last}), calculated using the linear trapezoidal rule
- t_{max} - the time to reach the observed maximum plasma concentration following a single dose
- λ_z - terminal elimination rate constant, calculated by log-linear regression of the terminal portion of the concentration time profile where there are sufficient data (a minimum of 3 plasma concentration values in the terminal log-linear phase, spanning an interval of at least 2 half-lives)
- $t_{1/2,\lambda_z}$ - half-life associated with the terminal slope (λ_z) of a semi logarithmic plasma concentration-time curve. Calculated as $\ln(2)/\lambda_z$

The secondary variables to be assessed for rosuvastatin metabolites N-desmethyl rosuvastatin and rosuvastatin lactone after multiple dosing are:

- $C_{ss,max}$ - maximum (peak) steady state drug concentration in plasma during steady state dosing interval
- $C_{ss,min}$ - minimum (trough) steady state drug concentration in plasma during steady state dosing interval
- $C_{ss,av}$ - average drug concentration in plasma during a dosing interval at steady station on administering a fixed dose at equal dosing intervals; calculated as AUC_{ss}/τ
- $t_{ss,max}$ - the time to reach the observed maximum plasma concentration at steady-state
- AUC_{ss} - area under the plasma concentration time curve during any dosing interval at steady state; calculated using the linear trapezoidal rule
- DF - degree of fluctuation; calculated as $(C_{ss,max} - C_{ss,min})/C_{ss,av} * 100\%$
- AR - accumulation ratio; calculated as $AUC_{(0-24)}(\text{Day 17})/AUC_{(0-24)}(\text{Day 1})$

Maximum concentration (C_{max}) and area under the concentration curve from zero to infinity (AUC) of rosuvastatin will be the primary variables for this study to summarize exposure in each subject. If AUC data cannot be determined in all subjects completing the study, area under the curve of plasma concentration against time from zero to last quantifiable concentration ($AUC_{(0-t)}$) will replace AUC as the primary variable.

CL/F

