Subjects will be admitted to the clinical research center (CRC) on Day -1. Day -1 assessments will be completed and blood will be collected for a pre-treatment (baseline) lipid profile. After an overnight fast, subjects will receive a 20 mg rosuvastatin calcium tablet on Day 1. Blood samples will be collected to 72 hours post-dose to assess the pharmacokinetic profile. On the morning of Day 4, (after the 72 hour blood collection) the subjects will again be dosed with 20 mg of rosuvastatin. The subjects will then be discharged from the CRC with study drug and instructions to take one 20 mg tablet of rosuvastatin calcium each morning for the next 2 days (Days 5-6). On the mornings of Days 7, 8, and 9 the subjects will return to the CRC to have blood collected for trough levels of rosuvastatin prior to dosing. After blood collection and dosing on Day 9, the subjects will leave the CRC with study drug and instructions to take one 20 mg tablet of rosuvastatin calcium each morning for the next 7 days (Days 10-16). The subjects will return to the CRC in the afternoon of Day 16 for readmission to the CRC. On the morning of Day 17, subjects will receive the last dose of 20 mg rosuvastatin calcium and blood samples will be collected to 24 hours post dose to assess the pharmacokinetic profile at steady-state. On Day 18, final assessments, including a blood sample to assess post-treatment lipid profiles, will be completed and the subjects discharged from the study.

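### Section 6.1.1 misstates two descriptive single-dose parameters: Vd/F lacks a bracket, and MRT read literally divides an AUMC with no tail term by an AUC extrapolated to infinity

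*Protocol*

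**What the plan says.** All the definitions stand together in protocol section 6.1.1, under the single-dose variables for rosuvastatin.

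- AUC is AUC(0-t) "and then extrapolated to infinity by the addition of" Clast/λz.
- AUC(0-t) is "area under the plasma concentration time curve from time zero to the last quantifiable plasma concentration (C_{last}), calculated using the linear trapezoidal rule".
- AUMC is "area under the first moment curve; AUMC will be calculated by the linear trapezoidal rule". No upper limit and no tail term are given.
- MRT is "mean residence time; calculated as $AUMC/AUC".
- CL/F is "apparent oral clearance, calculated as Dose/AUC (rosuvastatin only").
- Vd/F, described as the apparent volume during the terminal (λz) phase, is "calculated as $\text{Dose}/AUC * \lambda_z".

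The last single-dose sample is at 72 h: "Blood samples will be collected to 72 hours post-dose to assess the pharmacokinetic profile" (section 3.1).

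MRT and Vd/F appear in the list headed primary variables after a single dose, in the synopsis and in 6.1.1. The end of 6.1.1 then names Cmax and AUC of rosuvastatin, with AUC(0-t) as fallback, as the primary variables of the study. Section 6.4.3.3 lists the PM versus EM comparisons: geometric mean ratios of AUC, AUC(0-t) and Cmax, metabolite-to-parent ratios, and the difference in half-life.

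**The concern.** The section states the tail explicitly for AUC and gives none for AUMC, which gets the same trapezoidal rule as the truncated AUC(0-t). A trapezoidal rule ends at the last sample. AUMC/AUC on that basis is neither MRT over the observed interval nor MRT to infinity. It is always too low, and by more as the half-life lengthens or the last quantifiable sample comes earlier.

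For Vd/F, terminal-phase volume is clearance divided by λz. The printed expression multiplies by λz. The error is not a constant scale factor, because λz differs between subjects. A literal calculation would therefore distort the group summaries as well as the absolute level.

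At stake are the descriptive summaries of two parameters, and agreement between the protocol's definitions and whatever the study report presents.

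**Working it through.** The protocol states no figure for either parameter, so there is nothing to reproduce first. The check is one of dimensions plus a numerical example.

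**Vd/F**

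CL/F = Dose/AUC has units of volume/time, and λz has units of 1/time.

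- As printed: (Dose/AUC) × λz = (CL/F) × λz, in volume/time².
- Terminal-phase volume: Dose/(AUC × λz) = (CL/F)/λz, in volume.
- Printed over correct = λz²; correct over printed = 1/λz².

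With λz = ln(2)/half-life, 1/λz² (in h²) is 300 at 12 h, 751 at 19 h, 1199 at 24 h and 1873 at 30 h.

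The section's own notation does not supply the bracket. The DF entry, "degree of fluctuation; calculated as" (Css,max − Css,min)/Css,av * 100%, has the same a/b * c form and makes sense only from left to right.

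Effect on a group ratio: suppose PMs had CL/F and λz both at 0.8 of the EM values, with equal volume. The true PM/EM ratio of Vd/F is 0.8/0.8 = 1.0; the printed formula gives 0.8 × 0.8 = 0.64.

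**MRT**

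Inputs from the protocol: Day 1 sampling times of 0, 0.5, 1, 2, 3, 4, 5, 6, 8, 10, 12, 18, 24, 30, 36, 48, 54, 60 and 72 h (Table 1, Table 3), and the linear trapezoidal rule.

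Assumptions, since the protocol gives no values: one-compartment oral profile without noise, F·Dose/V = 1, absorption rate ka = 0.4 per h, all samples to 72 h quantifiable, half-life varied.

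- As written, literally: MRT = AUMC(0-t) / [AUC(0-t) + Clast/λz].
- Complete: AUMC(0-inf) = AUMC(0-t) + Clast·tlast/λz + Clast/λz², and MRT = AUMC(0-inf)/AUC.

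Worked case, half-life 19 h:

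- λz = 0.0365 per h, AUC(0-t) = 25.30, Clast = 0.0796, Clast/λz = 2.18, so AUC = 27.48.
- AUMC(0-t) = 601.0; tail terms 157.1 + 59.8 = 216.9, so AUMC(0-inf) = 817.8 (sum of unrounded values).
- As written: 601.0/27.48 = 21.9 h. Complete: 817.8/27.48 = 29.8 h. Shortfall 26.5%.

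| Half-life (h) | MRT as written (h) | MRT complete (h) | Shortfall |
|---|---|---|---|
| 5 | 9.7 | 9.7 | 0.1% |
| 10 | 16.1 | 16.8 | 4.2% |
| 12 | 18.1 | 19.7 | 8.2% |
| 19 | 21.9 | 29.8 | 26.5% |
| 24 | 22.6 | 37.0 | 38.8% |
| 30 | 22.5 | 45.7 | 50.7% |

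Values of ka from 0.3 to 1.0 per h change the shortfall by less than one percentage point. The complete formula recovers the model's true MRT, 1/λz + 1/ka, to within about 1%. An earlier last quantifiable sample enlarges the error: at a half-life of 20 h with the last sample at 48 h (ka 0.5 per h) it is 51%.

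The table stops below the longest half-life that could be estimated at all. Section 6.1.1 requires λz to span at least two half-lives, and 72/2 = 36 h.

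**The case against.** **The truncation of AUMC is inferred.** The protocol writes (0-t) and names the last quantifiable concentration where it means a truncated area, and AUC without a subscript means zero to infinity. By that convention AUMC without a subscript could also mean zero to infinity, with the tail left unstated. This stands in part: truncation is the literal reading, not the only one. The text still needs the tail, because the neighbouring AUC entry gives one and AUMC does not.

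**The intent for Vd/F is plain.** The entry calls it a terminal-phase volume, and CL/F stands directly above. An analyst would supply the bracket, and standard non-compartmental software may well output the usual quantity. This also stands. A reader might infer that reported volumes will be wrong by a factor of 300 to 1900; nothing in the protocol shows that. What is wrong is the specification.

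**No planned comparison uses either parameter.** A reader might infer that the PM versus EM contrast is compromised. Under the model above, half-lives of 19 and 24 h give a true MRT difference of 7.2 h, of which the literal formula shows 0.8 h. But section 6.4.3.3 plans no comparison of MRT or Vd/F, and the protocol gives no support for a half-life contrast of that size: section 1.2 says CYP2C19 has not been identified as the primary metabolic pathway. This objection stands in full.

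**The size of the MRT error is not known.** With a half-life of 10 h or less and samples quantifiable to 72 h, it is about 4% or smaller.

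**Conclusion.** Both definitions are wrong as written and should be corrected, as a minor matter. The Vd/F point is firm and needs no assumption: without the bracket the expression is not a volume. The MRT point holds on the literal reading. Its size runs from about 0.1% to 51% for half-lives of 5 to 30 h, and rests on an assumed half-life, a one-compartment profile and quantifiable samples to 72 h.

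The word primary over the parameter list might suggest that the main result is affected. It is not. The study-level primary variables are Cmax and AUC, with AUC(0-t) as fallback. None of the planned PM versus EM comparisons uses AUMC, MRT or Vd/F, and section 6.4.4 describes the study as exploratory with no hypothesis-based sample size. Nor do the documents show that reported values would be wrong, since the software may produce the standard quantities. In that case the protocol merely misdescribes them.

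**What to change.** In section 6.1.1:

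- Define AUMC(0-inf) = AUMC(0-t) + Clast·tlast/λz + Clast/λz², with AUMC(0-t) by the linear trapezoidal rule, and MRT = AUMC(0-inf)/AUC.
- Write Vd/F = Dose/(AUC·λz), with the bracket.

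Use the same formulas in the SAP. The cost is two lines of text, with no extra samples and no change to the planned comparisons.
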